22.5 Guidance on Collecting VAS Pain Score and Frequency of Pain Attacks Information

The Izbicki Pain Scale incorporates the following four elements in its measurement of pain:

- 1) patient self-estimation of intensity of pain using a visual analog scale (VAS)
- 2) the frequency of pain attacks
- 3) analgesic medication usage
- 4) the time of disease-related inability to work

The sum of the rank values divided by four gives the final value of the pain score. Please see Appendix 22.1 for more information. The Izbicki Pain Scale will be collected at every study visit. The information below will serve as guidance when collecting information for the first two elements of the Izbicki Pain Scale.

When reporting pain via VAS for the first element of the Izbicki Pain Scale, patients will be asked to report on the average pain experienced since the prior study visit. For the second element of the Izbicki Pain Scale, patients will be asked to report the average frequency of pain attacks experienced since the prior study visit. The manner in which these two questions are posed will depend upon the patient's pain pattern.

What is the patient's pain pattern?

Short and relapsing episodes of pain separated by periods of pain remission	Prolonged periods of fairly constant pain	Unknown or indistinguishable pattern of pain

1st Study Visit Within the previous three months, how strong was your most severe bout of pain? & Within the previous three months, how frequently did you experience a bout of pain?
 
Follow-up Study Visit Since the last study visit, how strong was your most severe bout of pain? & Since the last study visit, how frequently did you experience a bout of pain?
	
1st Study Visit Within the previous three months, how would you score the average level of pain you experienced? & Within the previous three months, how frequently have prolonged periods of pain occurred?
 
Follow-up Study Visit Since the last study visit, how would you score the average level of pain you experienced? & Since the last study visit, how frequently did prolonged periods of pain occur?
	
1st Study Visit Within the previous three months, how would you score your pain? & Within the previous three months, how frequently have you experienced pain?
 
Follow-up Study Visit Since the last study visit, how would you score your pain? & Since the last study visit, how frequently have you experienced pain?

August 28, 2017

Boston Scientific
WallFlex Pancreatic Pivotal Protocol
91067616 Rev/Ver AK
Page 64 of 64

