5.2 Exclusion Criteria

Patients who meet any one of the following criteria will be excluded from this clinical study.

1. Pancreatic or peri-ampullary cancer with or without pancreatic duct strictures caused by malignancy
2. Biliary strictures caused by chronic pancreatitis that are symptomatic and/or in need of therapeutic intervention
3. Perforated duct
4. Ansa pancreatica
5. Presence of pancreatic cysts suspected to be cystic tumor or requiring transmural drainage
6. Duodenal/groove pancreatitis
7. Autoimmune pancreatitis
8. Pancreatic duct stenoses not located in the head of the pancreas
9. Failed access during an attempted ERCP on a prior date at the investigational center
10. Duration of indwell of one single plastic pancreatic stent or cumulative duration of consecutive single plastic pancreatic stents immediately prior to study stent placement exceeding 90 days
11. History of prior single pancreatic plastic stent(s) followed by a stent-free period shorter than 1 year before enrollment into the study
12. History of prior side-by-side multiple pancreatic plastic stents up to one year prior to enrollment
13. History of prior pancreatic metal stent(s)
14. Reported recent history of acute relapsing pancreatitis in the absence of chronic pancreatitis
15. Patients for whom endoscopic techniques are contraindicated.
16. Patients who are currently enrolled in another investigational study that would directly interfere with the current study, without prior written approval from the sponsor
17. Inability or refusal to comply with the follow-up schedule including patient living at such a distance from the investigational center that attending follow-up visits would be unusually difficult or burdensome

August 28, 2017

Boston Scientific
WallFlex Pancreatic Pivotal Protocol
91067616 Rev/Ver AK
Page 24 of 64

6 Patient Accountability

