7.1 Data Collection

Procedure/Assessment	Screening/ Baseline	Study Stent Placement****	Month 1 (30 ± 5 Days)	Month 3 (90 ± 10 Days)	Month 6 Study Stent Removal (180 ± 15 Days)	Month 3 Post-Removal Follow-up Visit (90± 15 Days)	Month 6 Post-Removal Follow-Up Visit (180 days ± 15 days)
Informed consent form, including informed consent signature date	X						
Demographics and Medical and EPS History	X						
Weight*	X	X	X	X	X	X	X
EPS		X (if required)					
Pre-stenting pancreatic stone clearance (as applicable)	X***	X					
Study Stent Placement		X					
Study Stent Removal					X		
Pancreatic Duct Imaging (may be non-invasive)	X***	X Pre- and Post- Stent Placement			X** Post-Stent Removal		X
Pain Score, Average Daily Narcotic Dose, and QOL Score*	X	X (prior to all stent procedures)	X	X	X (prior to stent removal)	X	X
Adverse Event Assessment	X***	X	X	X	X	X	X
Concomitant Medications, including injectable narcotics	X	X	X	X	X	X	X

* Weight Pain Score and QOL must be assessed at all visits, including any unscheduled visits.

**Window for imaging is ±4 weeks.

***Applicable at Baseline visit for patients who undergo plastic stent placement for ESWL per inclusion criteria 9.

****Study Stent Placement visit may take place on the same day as Screening/Baseline, if deemed appropriate by the treating physician

Boston Scientific
WallFlex Pancreatic Pivotal Protocol
91067616 Rev/Ver AK
Page 27 of 64

August 28, 2017

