For the patients who have a single plastic stent in place for up to 90 days before receiving the study stent, inclusion criteria #6 and #7 will be reassessed immediately prior to the plastic to study stent exchange. Patients who do not meet the inclusion criteria levels of the VAS pain score (≥ 20) and frequency of pain score (50, 75, or 100) at the time of stent exchange will be excluded from the primary effectiveness endpoint analyses but will be included in the primary safety endpoint analysis and all secondary endpoint analyses. For the patients who meet the inclusion criteria levels, we will use the scores (VAS Pain Score and Frequency of Pain Score) collected immediately prior to the plastic to study stent exchange as their baseline and include them in the primary effectiveness endpoint analyses.

Primary Safety Endpoint:

August 28, 2017

Boston Scientific
WallFlex Pancreatic Pivotal Protocol
91067616 Rev/Ver AK
Page 32 of 64

Rate of related Serious Adverse Events (SAEs) from WallFlex Pancreatic stent placement to end of study.

Relatedness will be determined by the PI, reporting if the SAE is related to the study stenting procedure, to the indwelling study stent, to study stent removal and/or to study stent migration.

Pain thought to be caused by WallFlex Pancreatic stent expansion will be reported, but will not count towards the endpoint if all three of the following conditions apply:⁵

1. Pain can be managed by medication, with the exception of injectable narcotic use for more than 24 hours.
2. Pain does not cause WallFlex Pancreatic stent removal.
3. Pain resolves by 72 hours after WallFlex Pancreatic stent placement.

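### When a patient already carrying a plastic stent is screened and exchanged on the same day, the pre-exchange pain re-check uses a three-month recall that can include pain from before the plastic stent

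*Combined protocol and SAP*

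**What the plan says.** Section 8.1.1 states that for patients with a plastic stent in place "inclusion criteria #6 and #7 will be reassessed immediately prior to the plastic to study stent exchange". Patients below the required VAS and frequency levels at that moment "will be excluded from the primary effectiveness endpoint analyses but will be included in the primary safety endpoint analysis". Those who meet the levels enter the effectiveness analysis with the scores "collected immediately prior to the plastic to study stent exchange as their baseline". The section gives no recall period.

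The question wording is in Appendix 22.5. At a first study visit, the column for relapsing pain asks "Within the previous three months, how strong was your most severe bout of pain" and "Within the previous three months, how frequently did you experience a bout of pain". At later visits the severity question becomes "Since the last study visit, how strong was your most severe bout of pain". The column for fairly constant pain asks for an average level, and the third column specifies neither worst nor average. All three use the same two recall windows. Section 7.4.1 asks for average pain since the prior visit, which defines no window when there is no prior visit.

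Inclusion criteria 4 to 7 (section 5.1) provide for patients who already have a plastic stent. Exclusion 10 (section 5.2) rules out a plastic stent indwell "immediately prior to study stent placement exceeding 90 days". A footnote in section 7.1 says "Study Stent Placement visit may take place on the same day as Screening/Baseline", and section 7.6 repeats this.

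**The concern.** The re-check exists because section 8.1.2 expects 20% to 30% of patients to fall below the pain levels on account of a prior plastic stent. To identify them, the pre-exchange score must describe pain with the plastic stent in place.

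One permitted visit pattern breaks this link: the plastic stent was placed before consent, and Screening/Baseline and the exchange fall on one day. The exchange is then the first study visit and the script looks back three months. Whatever part of that window precedes the plastic stent is a period in which, to be eligible, the patient had a VAS of at least 20 and pain at least weekly. A worst-bout question over such a window can return the pre-stent pain.

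Two things follow for such a patient. Someone whom section 8.1.1 means to exclude may be kept, and the baseline against which the 50% reduction is judged is too high. Both push towards success, and a single-arm comparison with a fixed goal has no control arm to absorb the shift.

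**Working it through.** **1. The plan's own figures.** Exact one-sided binomial test, goal 53%, assumed rate 75%, alpha 0.025 (section 8.1.2). With N = 43 the test rejects at 30 or more successes: P(X ≥ 30 | 0.53) = 0.019, and power P(X ≥ 30 | 0.75) = 0.834. The stated 43 is reproduced as the smallest N from which power stays at or above 80%. The enrolment figures also reproduce: 57/0.9 = 63.3, rounded up to 64; 64/0.7 = 91.4, rounded up to 92.

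**2. Which question applies at the exchange.**

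| Route | Exchange visit is | Recall window |
|---|---|---|
| Plastic stent placed in-study at Baseline for ESWL (section 7.5) | a later visit | since the last study visit: the plastic-stent period |
| Arrives stented, separate earlier Baseline | a later visit | since the last study visit: entirely on the plastic stent |
| Arrives stented, Baseline and exchange on the same day | the first study visit | previous three months |
| Same, but placement counted as a follow-up visit | a same-day later visit | about zero days |

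Only the last two rows are a problem. The documents do not say which of them applies.

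**3. How much of the window precedes the plastic stent.** Pre-stent days = window (three months, 90 to 92 days) minus indwell.

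| Indwell | Pre-stent days | Share of window |
|---|---|---|
| 30 days | 60–62 | about 67% |
| 60 days | 30–32 | 33–35% |
| 90 days | 0–2 | 0–2% |

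**4. One patient (assumed scores; scale from Appendix 22.1, responder rule from section 8.1.1).**
- On the plastic stent: VAS 10, pain several times a year (25). Score (10 + 25)/2 = 17.5. Both elements are below the re-check levels, so the patient should be excluded.
- Three-month worst-bout recall: VAS 60, several times a week (75). Score (60 + 75)/2 = 67.5. The patient passes, and the partial-relief threshold is 67.5/2 = 33.75.
- Six months after removal: score still 17.5. The reduction is 1 − 17.5/67.5 = 74%, which counts as partial relief although nothing has changed from the pre-exchange state.

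**5. Effect on the test (illustration).** Assume 64 properly included patients at a true 53%, plus k wrongly kept patients who succeed with probability s. Chance of passing = P(Bin(64, 0.53) + Bin(k, s) ≥ c), where c is the exact critical count for 64 + k. With k = 0, c = 43 and the chance is 1.5%.

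| k | c / N | s = 66% | s = 80% | s = 90% |
|---|---|---|---|---|
| 5 | 46/69 | 2.2% | 3.1% | 3.9% |
| 10 | 49/74 | 3.0% | 5.7% | 8.6% |

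The 66% is the plan's pooled plastic-stent estimate (section 8.1.2). The 80% and 90% have no source in the documents, and neither does k. If all N patients succeeded at 53%, the chance would also be 1.5% at N = 69 and at N = 74, so the rise is not an artefact of the larger N.

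**The case against.** The strongest reply is that the gap is narrow. The plastic-stent route the protocol describes in most detail, placement at Baseline after ESWL, gets the right question, and so does anyone with a separate Baseline visit. Same-day placement is allowed only where the treating physician thinks it appropriate, and its frequency is not stated. This stands and limits the size of the point.

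A second reply is that the schedule gives Baseline and placement separate pain scores, that section 8.1.1 speaks of levels at the time of exchange, and that Appendix 22.5 is guidance, so the intent is current pain. The intent is clear enough. But Appendix 22.5 is the only place with question wording, and nothing limits recall to the plastic-stent period. Counting placement as a follow-up visit leaves about zero days to recall.

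Third, the bias varies. It nearly vanishes as indwell approaches 90 days and is diluted where the script asks for an average level. This also stands.

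A reader might infer that the re-check fails altogether, or that neither question captures pain on the plastic stent. The documents do not support either: the first two routes in the table work, and a three-month window includes the stented period. Nor can the example patient's success be called free of any study-stent effect. The endpoint falls 6 months after removal of a stent intended to stay 6 months, and a society report quoted in section 1.1 puts about half of pancreatic stents occluded by 4 weeks. The example shows only a success without change from the pre-exchange state.

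**Conclusion.** The concern holds for one group: patients who arrive with a plastic stent in place, have Baseline and exchange on the same day, and have an indwell well short of 90 days. For them the re-check can keep patients it is meant to exclude and give them an inflated baseline, most clearly under the worst-bout wording. The direction is towards success against 53%.

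The size cannot be fixed from the documents. The range of 2.2% to 8.6%, against 1.5%, rests on an assumed 5 to 10 wrongly kept patients and an assumed success rate of 66% to 90%. At 66%, five such patients leave the test within its nominal 2.5%; ten take it to 3.0%.

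A reader might go further and take the lower end of the expected re-check failures, 20% of 92 or about 18 patients. With 18 wrongly kept the chance of passing is 6.6% at a 66% success rate and 17% to 29% at 80% to 90%, against 2.2% for 82 patients all at 53%. That is not a supported estimate: the expected failures come from every route, and nothing suggests they would all be same-day patients recalling pre-stent pain.

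The passage is worth correcting because a written script, followed as it stands, can give a wrong inclusion and a wrong baseline.

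**What to change.** In Appendix 22.5, add a row for any patient with a plastic stent in place at study stent placement: the pre-exchange VAS and frequency questions cover only the time since plastic stent placement, even when this is the first study visit. In section 8.1.1, add a sentence that this score is used for the re-check and as the baseline, and is kept separate from the pre-plastic score that criterion 4 already requires. Align section 7.4.1 with the same window.

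The cost is one script row and one sentence, with the matching edit in 7.4.1, and no extra visit. The small downside is that a few more patients will be excluded from the effectiveness analysis.

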7.4 Scoring System

7.4.1 Izbicki Scoring System

The Izbicki Pain Scale incorporates four elements: 1) patient self-estimation of intensity of pain using a visual analog scale (VAS), 2) the frequency of pain attacks, 3) analgesic medication usage and 4) the time periods of inability to work. The sum of the rank values divided by four gives the final value of the pain score. See Appendix 22.1 for the Pain Scale.

Patients will be asked to report on the average pain experienced since the prior visit when reporting pain via VAS for the first element of the Izbicki Pain Scale. Patients will be asked to report the average frequency of pain attacks experienced since the prior visit for the second element of the Izbicki Pain Scale. Please see Appendix 22.5 for further guidance on collecting the VAS and frequency of pain attacks information.

Note: For centers with medication types that do not align with section 3 of the Izbicki Pain scale, relevant corresponding medication types may be made available for scoring.

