8.1 Endpoints

8.1.1 Primary Endpoint

Primary Effectiveness Endpoint:

Pain Reduction

Pain reduction will be assessed at 6 months post-stent removal or 6 months post-observation of complete or partial stent migration compared to pain collected at baseline. Baseline for patients without a plastic pancreatic stent immediately prior to study stent placement will be at the time of enrollment. Baseline for patients with a plastic pancreatic stent immediately prior to study stent placement will be at the time of study stent placement.

Pain will be scored between 0 and 100 as the mean of the VAS Pain Score and Frequency of Pain sectors of the Izbicki pain scale.

Complete pain relief is defined as pain score ≤ 10 , and partial pain relief is defined as pain score > 10 and reduced by at least 50% compared to baseline.

Complete or partial pain relief in the setting of a 50% higher average daily narcotic dose will be considered a primary effectiveness endpoint failure. Average daily narcotic dosage for prior month will be assessed at baseline visit prior to plastic or study stent placement, whichever is implanted first, and at 6 months post-stent removal/observation of complete distal migration.

Patients who experience stent migration in setting of recurring pain (VAS Pain Score of ≥ 20) will be considered as having failed the primary effectiveness endpoint.

Patients who are restented in the setting of recurring pain will be considered as having failed both the primary effectiveness endpoint and the secondary stricture resolution endpoint and may only be restented with a non-study stent.

Restenting with a new study stent may only occur during the initial stent placement procedure for such situations as stent misplacement, improper stent size choice, or other conditions, as necessary and will not be considered a primary effectiveness endpoint failure or a secondary effectiveness stricture resolution endpoint failure.

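### Sections 7.4.1 and 22.5 disagree on what the pain VAS records, and nothing keeps a patient's baseline question form in use at the 6-month assessment.

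*Combined protocol and SAP*

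**What the plan says.** Section 7.4.1 defines the VAS item: "Patients will be asked to report on the average pain experienced since the prior visit when reporting pain via VAS". The lead text of Appendix 22.5 repeats it: "patients will be asked to report on the average pain experienced since the prior study visit". The appendix then adds "The manner in which these two questions are posed will depend upon" the patient's pain pattern, and gives three columns of questions:

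- **Short, relapsing episodes.** The follow-up VAS question is "Since the last study visit, how strong was your most severe bout of pain". The frequency question is about bouts.
- **Prolonged, fairly constant pain.** The VAS question is "Since the last study visit, how would you score the average level of pain you experienced". The frequency question is "Since the last study visit, how frequently did prolonged periods of pain occur".
- **Unknown pattern.** The patient scores the pain, with neither worst nor average specified. The frequency question is about any pain.

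First-visit questions look back three months and follow-up questions look back to the last study visit. Sections 7.1 and 7.11 require a pain score at unscheduled visits too.

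Under 8.1.1 the primary effectiveness score is the mean of these two items. A patient succeeds with a score of 10 or less, or with a score above 10 that is "reduced by at least 50% compared to baseline". The test in 8.1.2 compares the success rate with a fixed goal of 53% in a single arm.

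**The concern.** Worst pain and average pain are different quantities. The statement that the wording follows the pain pattern explains why there are three forms. It does not reconcile a most-severe-bout question with two statements that the VAS is an average.

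The conflict reaches the endpoint through a gap. No text says at which visit the pattern is judged, or that the form used for the baseline score is used again 6 months after removal. Treatment meant to relieve pain can plausibly turn constant pain into occasional bouts. A site that follows the pattern at each visit would then change form, and the 50% rule would compare an average with a worst, or the reverse.

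With one arm and a fixed goal, no control group offsets a net shift. The same VAS also feeds the threshold of 20 used for eligibility, for the reassessment at stent exchange and for the migration failure rule.

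**Working it through.** **1. The plan's own figure.** Exact one-sided binomial test, null 53%, assumed rate 75%, alpha 0.025 (8.1.2). At n=43 success needs at least 30 responders, with type I error 1.90% and power 83.4%. At n=42 power is 76.6%. The stated 43 is reproduced as the size from which power stays at or above 80%. Allowing 10% loss on the safety requirement, 57/0.90 = 63.3, gives 64.

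**2. Effect of the form on one patient.** Score = (VAS + frequency)/2, with frequency 0, 25, 50, 75 or 100 (22.1). The patient values are assumed.

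| | Baseline | 6 months, form kept | 6 months, form switched |
|---|---|---|---|
| Constant pain at baseline | average 60, frequency 100: 80 | average 15, frequency 50: 32.5, -59%, success | worst 60, frequency 50: 55, -31%, failure |
| Relapsing pain at baseline | worst 80, frequency 75: 77.5 | worst 50, frequency 50: 50, -35%, failure | average 20, frequency 50: 35, -55%, success |

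Within each row the 6-month frequency is the same under both forms, so the VAS form alone changes the outcome. It can do so in either direction.

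**3. Recall of the 6-month score.** Visit windows are from 7.9 and 7.10.
- On schedule: shortest 165 - 105 = 60 days; longest 195 - 75 = 120 days.
- 3-month post-removal visit missed: back to the removal visit, 165 to 195 days.
- Unscheduled visit counted as the last study visit: shorter, with no lower limit stated.

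**4. Hypothetical error rates.** The documents give no rate of form changes or of changed outcomes. Let a share f of true non-responders flip to success when the true rate is 53%. The observed rate is then p = 0.53 + 0.47f, and f is solved for P(X at or above the critical value) = 0.025.

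| n | Success at | Type I error, f=0 | f at which it reaches 2.5% |
|---|---|---|---|
| 64 | 43 | 1.50% | 2.8% |
| 57 | 39 | 1.31% | 3.7% |
| 43 | 30 | 1.90% | 1.9% |

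At n=64 about 64 x 0.47 = 30.1 non-responders are expected, and 2.79% of them is 0.84 of a patient.

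If flips are equal in both directions at 2%, 5% or 10% (n=64):
- Under the null, p = 0.53(1-f) + 0.47f = 0.5288, 0.5270, 0.5240. Type I error falls to 1.4%, 1.3%, 1.2%.
- At a true 75%, p = 0.75(1-f) + 0.25f = 0.740, 0.725, 0.700. Power falls from 94.0% to 91.4%, 86.2%, 73.8%.

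If only responders are lost, p = 0.75(1-f), and power drops below 80% once f exceeds about 5.1%.

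**The case against.** The best defence is the layout of 22.5. Each column pairs the first-visit and follow-up questions on the same construct, worst with worst and average with average. If a patient stays in one column, the ratio compares like with like, and tailoring the question to the pattern is reasonable. No passage tells a site to reclassify. This stands: the contradiction by itself does not bias the endpoint. It does not close the gap, because keeping the column is an inference from a table while the written instruction ties the wording to the pattern.

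Four stronger readings are tempting and are not supported:

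- **That no recall window is stated.** It is: since the last study visit. Only its length is left open. For scores "collected immediately prior to the plastic to study stent exchange as their baseline", the follow-up wording gives roughly the 30 to 90 days of plastic stenting if that stent was placed at the baseline visit.
- **That the frequency wording decides success.** A score of 10 or less does need frequency 0, since frequency 25 already gives 12.5. But partial relief counts equally as success, and the examples turn on the VAS form with frequency held fixed.
- **That the trial's type I error is inflated.** The error rates are generic misclassification curves. Symmetric flips lower type I error and cost power.
- **That every patient is exposed.** Patients restented for recurring pain, or with migration and a VAS of 20 or more, fail whatever the 6-month score, which limits part of the effect.

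**Conclusion.** The wording conflict and the missing rule on keeping the form are certain from the text. The possible effect on the primary endpoint is real: permitted readings of 22.5 can turn the same patient from success to failure or the reverse. Its size and direction cannot be derived from the documents. The 2.8% threshold at n=64 shows only that the margin is small, less than one patient in expectation, if flips run one way towards success. It assumes a true rate of exactly 53% and 64 analysed patients. The point should be fixed, but it does not show that the planned test is invalid, and it leaves 43, 57, 64 and 92 unchanged.

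**What to change.** 1. Make 7.4.1 and 22.5 agree on what the VAS measures. Pattern-specific questions can stay if 7.4.1 says so.
2. State that the pattern is classified at the visit that supplies the baseline score, and that the same VAS and frequency question form is used at the 6-month assessment.
3. Record the form on the eCRF at every visit. This matters also because 8.1.2 carries earlier scores forward when the 6-month score is missing.
4. State that unscheduled or missed visits do not change the recall period of the 6-month score. One option is the previous three months, as at the first visit; at the earliest visit this starts about day 165 - 90 = 75 after removal.
5. For patients whose baseline is already collected, keep the frequency wording used at baseline. Changing it mid-study would create the very mismatch at issue.
6. Keep patients with a changed or unrecorded form in the primary analysis. Add a sensitivity analysis that counts their successes as failures and reports how many reversals would overturn the result, in the manner of 8.1.3. At 0.75 x 64 = 48 successes, the result survives 48 - 43 = 5.

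The cost is a protocol amendment with the approvals in section 10, one eCRF field and one sensitivity analysis. That analysis may be uninformative if many earlier patients have no recorded form, and they should be reported as such. No visits are added.
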